4.2.2 Primary Economical Efficacy Variable

The second primary endpoint: **direct medical cost** associated with the surgery (time to perform surgery, number of wound dressings sessions and cost to treat complications) during the first year will be calculated for each subject using standard cost/unit for each participating country. This means that the direct medical costs are all health care costs, incurred, related to the procedure. The following subsection will define the guidelines for creating the direct medical cost tabulation.

4.2.2.1. Cost identification

All measured costs relating to the procedure and its complications will be identified and tabulated. In case of doubt, an independent physician will decide if certain costs should be included. The costs include, but are not limited to:

Surgery:

- The time to perform surgery, "skin to skin" time
- Type of anaesthesia at surgery
- Days in hospital due to surgery

Extra visits caused by wound dressings (check box):

- Number of extra visits due to Wound dressing
- Surgeon conducted the visit multiplied with Duration of extra visit
- Surgical nurse conducted the visit multiplied with Duration of extra visit
- Audiologist conducted the visit multiplied with Duration of extra visit
- Material used (will be listed and cost estimated)

Protocol:

Clinical and health economic evaluation with a new Baha abutment design combined with a minimally invasive surgical technique

Protocol No:

CBAS5439

Version:

1.0

Page 11 of
23

Extra visits caused by complications (check box):

- Number of extra visits due to Complication
- Surgeon conducted the visit multiplied with Duration of extra visit
- Surgical nurse conducted the visit multiplied with Duration of extra visit
- Audiologist conducted the visit multiplied with Duration of extra visit
- Material used (will be listed and cost estimated)

Concomitant therapy:

- A list of concomitant therapies will be reviewed and therapies identified as related to the surgery/implant and cost estimated. It is of importance that no double reporting of these costs and the material used (extra visit) cost will be made.

4.2.2.2. Estimating unit costs

In order to estimate the total cost of treatment for each subject, the respective quantities of resource use (e.g. surgery time, audiologist time, terra-cortril ointment) will be multiplied by their corresponding unit cost. These costs can differ between centers because of small changes in their practices or because of different unit prices (also see "Different countries").

When calculating the total cost per patient, the individual costs are specified and accumulated.

The unit costs of most items will be obtained from nationally or locally available sources. The study will calculate the costs for one jurisdiction at the time with the full data set of all countries accumulated. This will be done for each country (e.g. the study outcomes in Sweden with 106 subjects etc.).

4.2.2.3. Price year, inflation and discounting

Resources and costs were measured in the year in which they were analyzed. Costs were not revalued. Discounting was not performed because of the time frame being just one year.

4.2.2.4. Currency

All costs will be expressed in Euro's. When other currencies are applicable (Swedish Krona), the exchange rate used will be the exchange rate at the day of the database lock.

4.2.3 Secondary Clinical Efficacy Variables

4.2.3.1. The Holgers Index

The **Holgers Index** is designed to capture signs and symptoms of inflammation or infection at the site of implantation. The scale should be completed at visit 3-10.

The following scale will be used:

- | | |
|---|--|
| 0 | No irritation. Epidermal debris removed, if present |
| 1 | Slight redness. Local temporary treatment, if needed |
| 2 | Red and slightly moist tissue. No granulation formation, local treatment and extra controls as indicated |
| 3 | Reddish and moist; sometimes granulations tissue, revision surgery is indicated |
| 4 | Removal of the abutment / implant necessary due to infection |
| R | Removal of implant for reasons not related to skin problems |

Protocol:

Clinical and health economic evaluation with a new Baha abutment design combined with a minimally invasive surgical technique

Protocol No:

CBAS5439

Version:

1.0

Page 12 of
23

Holgers Index will also be categorised into 0-1 vs 2-4 (R) and 0 vs 1-4 (R) at each visit.

Max of Holgers Index per patient during the study will also be analysed.

Holgers Index according to AE reporting will also be analysed. If no stop date for an AE with Holgers Index is entered the AE is ongoing and should be counted from the start date and onwards.

4.2.3.2. *Soft tissue thickening/overgrowth*

In order to capture **soft tissue thickening/overgrowth** the following scale has been developed for this investigation. The scale should be completed at visit 3-10.

The following scale will be used:

- | | |
|---|--|
| 0 | No soft tissue thickening or overgrowth |
| 1 | Slight soft tissue thickening or overgrowth |
| 2 | Moderate soft tissue thickening or overgrowth. Local treatment and extra controls as indicated |
| 3 | Marked/distinct soft tissue thickening or overgrowth. Revision surgery is indicated. |

Max of the soft tissue thickening/overgrowth will be calculated for each patient.

4.2.3.3. *Wound healing*

At visit 3-7 determination if the **wound is healed or not** will be performed.

The **visible abutment length** will be measured at visit 3-10 and change from visit 3 will be calculated.

4.2.3.4. *Aesthetic outcomes*

The **aesthetic outcome** of the surgery will be evaluated by the subject and the surgeon at visit 6, 8 and 10. The scar will be evaluated in accordance with the Patient and Observer Scar Assessment Scale (POSAS) v 2.0 that consists of two parts, a patient scale and an observer scale:

- Patient items:
 - pain
 - itching
 - colour
 - stiffness
 - thickness
 - irregularity
 - overall opinion
- Observer items:
 - vascularity
 - pigmentation
 - thickness
 - relief
 - pliability
 - surface area and
 - overall opinion

STATISTISKA KONSULTGRUPPEN		Statistical Analysis Plan	
Protocol: Clinical and health economic evaluation with a new Baha abutment design combined with a minimally invasive surgical technique		Protocol No: CBAS5439	
		Version: 1.0	Page 13 of 23

4.2.3.5. Pain

At visits 3, 4, 5 and 7 the **pain** questions “Has the scar been painful the past few weeks?” and “Any neuropathic pain during the past weeks?” will be evaluated. At visit 6, 8 and 10 the pain questions in the POSAS observer scale will be used.

Pain (2 variables) will also be analysed in a categorical manner: 1, 2-3, 4-6 and 7-10.

Max pain (2 variables) per patient will be analysed.

Max pain (2 variables) will also be analysed in a categorical manner: 1, 2-3, 4-6 and 7-10.

4.2.3.6. Numbness

Subjects will be asked if they experience any **numbness** (No numbness, Numbness within 2 cm from the abutment, Numbness within and beyond 2 cm from the abutment) around the abutment at visit 3-10.

Also **Max of the numbness score** for each patient will be analyzed.

4.2.3.7. Surgical time

Surgical time (min) will be analysed.

4.2.4 Secondary Economical Efficacy Variables

4.2.4.1. Direct medical costs by component

The components (Surgery, Wound dressings, Complications and Concomitant therapy) of **Direct medical costs** will also be analysed.

4.2.5 Tertiary Clinical Efficacy Variables

The **Health Utilities Index (HUI-III)** dimensions (3-6 levels) and HRQL (Hearing related quality of life) score at visit 1, 7, 8 and 10 and change from visit 1:

- vision
- hearing
- speech
- ambulation/mobility
- pain
- dexterity
- self-care
- emotion and
- cognition

Coding will proceed according to the HUI-III coding and procedure manual². The attribute levels, single-attribute utility scores, overall health-state vector and overall HRQL utility scores will be calculated according to this instruction.

4.2.5.1. APHAB

Abbreviated Profile of Hearing Aid Benefit (APHAB), unaided and aided, scores at visit 1 (only unaided), 7 8, and 10 and difference between aided at visit 7, 8 and 10 and unaided at visit 1 will be computed:

Protocol:

Clinical and health economic evaluation with a new Baha abutment design combined with a minimally invasive surgical technique

Protocol No:

CBAS5439

Version:

1.0

Page 14 of
23

- Ease of Communication
- Reverberation
- Background Noise
- Aversiveness
- Global Score

4.2.5.2. Sound processor usage

Use of sound processor will be presented at visit 5 to 10:

- Number of hours per week will be calculated from the CRF fields Number of days of use per week and Number of hours of use per day
- Type of sound processor used

Non-usage (less than one hour of Baha usage per week) at more than one visit will be analysed.

4.2.5.3. Implant stability

Implant Stability Quotient (ISQ) High and Low will be presented at surgery as a baseline value and at visit 2-10. Change from Surgery will also be calculated. Mean ISQ AUC₀₋₁₂ months, Mean ISQ AUC₀₋₂₄ months and Mean ISQ AUC₀₋₃₆ months will be calculated for subjects without abutment changes.

4.2.5.4. Smoking habits and snuff

Smoking habits (No, Smoking - Less than 10 cigarettes/day, Smoking - Between 11 and 20 cigarettes/day, Smoking - Between 21 and 40 cigarettes/day, Smoking - More than 40 cigarettes/day) at visits 1, 4, 6, 8, 9 and 10.

Snuff (Yes/No) and number of cans per month (for Swedish patients only) at visits 1, 4, 6, 8, 9 and 10.

4.2.5.5. Additional surgical variables

Additional information recorded during **surgery**:

- Type of surgery
- Skin thickness (test group only)
- Length of the abutment

4.2.5.6. Variables for the cost consequence analysis

- HUI-III utility scores will be calculated before surgery, at 24 weeks, at 12 months after surgery. The HUI-III QALY over 1 year will be calculated using the following AUC method: multiplying the average utility of two subsequent measurements with the time interval, and adding up over both time intervals. In case of missing values prior to surgery, the mean of patients with a similar aetiology (SSD, mixed, conductive) will be used. In case of a missing value at 6 months, this will be interpolated with the 1 year value. In case of a missing value at 1 year, the last observation carry forward (LOCF) technique will be used. In case of extra measurements, these will be added to the AUC calculation. In case of an implant and/or permanent abutment extrusion or removal, the last unaided HUI-III will be used to portray the last health state without the Baha, unless an extra HUI-III was performed to portray this health state.
- The unaided Global APHAB score before surgery and afterwards aided global APHAB score over the first year (AUC) will be calculated per patient. In case of

Protocol:

Clinical and health economic evaluation with a new Baha abutment design combined with a minimally invasive surgical technique

Protocol No:

CBAS5439

Version:

1.0

Page 15 of
23

missing values prior to surgery, the mean of patients with a similar aetiology (SSD, mixed, conductive) will be used. In case of a missing value at 6 months, this will be interpolated with the 1 year value. In case of a missing value at 1 year, the LOCF technique will be used. In case of extra measurements, these will be added to the AUC calculation. In case of an implant and/or permanent extrusion or abutment removal, the last unaided APHAB global score will be used.

- The POSAS before surgery can be presumed to be the lowest value (1) and afterwards the POSAS over the first year (AUC) will be calculated per patient. Same imputation rules as in APHAB and HUI-III will be made here.
- The course of adverse soft tissue reactions will be calculated over the first year (AUC) per patient as measured by the Holgers Index taken from AE page and from visits. The Holgers index will be carried forward up to next change of Holgers index (at an ordinary visit or an extra visit due to an AE with Holgers). AUC ($y = \text{Holgers severity (0-4)}$, $x = \text{day 0 - 365}$). If no stop date for an AE with Holgers Index is entered, the AE is ongoing and should be counted from the start date and onwards. Sensitivity analyses of the carry forward for of Holgers from visits and onward will be made as required.

The AUC of the APHAB and HUI-3 will be calculated using the assumption that the health state before and after surgery is similar until the audiological fitting occurred with the Baha. The individual Baha fitting time will be used to compensate for the variability in centers. After fitting the average will be calculated between this time point and 4 weeks later (which will be imputed with the value of 24 weeks). The time point between 24 weeks and 1 year will also be averaged. This accumulates to the AUC of the first year.

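### Two imputation rules for the 1-year QALY and APHAB AUC need tightening: the 24-week interpolation does not name its second anchor, and LOCF for HUI-III has no exception for death

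*SAP*

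**What the plan says.** SAP 4.2.5.6 defines the variables for the cost-consequence analysis. They sit under the tertiary variables (SAP 4.2.5) and are analysed in SAP 5.7.3.

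- **Timing.** "HUI-III utility scores will be calculated before surgery, at 24 weeks, at 12 months after surgery". APHAB is scheduled at the same visits, and only unaided at visit 1 (SAP 4.2.5.1).
- **First AUC method (HUI-III bullet).** A trapezoid: "multiplying the average utility of two subsequent measurements with the time interval, and adding up over both time intervals".
- **Second AUC method (closing paragraph, HUI-III and APHAB).** It assumes that "the health state before and after surgery is similar until the audiological fitting occurred with the Baha". The score is then averaged between fitting and a point "4 weeks later (which will be imputed with the value of 24 weeks". From 24 weeks to 1 year the two scores are averaged.
- **Missing 24-week score (also called 6 months in the section).** "In case of a missing value at 6 months, this will be interpolated with the 1 year value". The same rule is given for APHAB.
- **Missing 1-year score.** For HUI-III: "In case of a missing value at 1 year, the last observation carry forward (LOCF) technique will be used". For APHAB: "In case of a missing value at 1 year, the LOCF technique will be used".
- **Stated exception.** After extrusion or removal of the implant, or permanent loss of the abutment, "the last unaided HUI-III will be used to portray the last health state without the Baha", unless an extra questionnaire was completed. APHAB has a parallel rule. Death is not mentioned here; it appears only as a line in the adverse-event overview (SAP 5.8.2).

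**The concern.** Interpolation needs two points, and the SAP names one. Unless an extra measurement happens to exist, the only earlier score is the unaided one from before surgery. A straight line from there to 1 year treats the hearing benefit as a slow ramp over the whole year. The closing paragraph of the same section treats it as an early step, complete four weeks after fitting. Two programmers could therefore derive different QALYs from the same data.

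The LOCF rule covers every missing 1-year HUI-III score. The authors saw that losing the implant makes carry-forward wrong and wrote an exception for it, but they wrote none for death. Followed exactly, the rule credits utility to day 365 for someone who is no longer alive.

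A related gap arises when both follow-up scores are missing. LOCF then carries the unaided pre-surgery score through the year, so no aided gain is counted, and the SAP does not say whether this is intended.

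At stake are the between-group tests of the HUI-III QALY and APHAB AUC, and the cost-consequence estimates with their 95% confidence intervals.

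**Working it through.** The SAP gives no numerical QALY or APHAB AUC, so there is no figure to reproduce. The check applies its rules to one patient.

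**Inputs from the documents:** scores at 0, 24 and 52 weeks (SAP 4.2.5.6); planned fitting at week 3, with delay allowed (protocol 6.4); 53 subjects randomised per group (protocol 9.2.2, SAP 2.4.2).

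**Assumptions not in the documents:** aided-minus-unaided gain g constant from 24 weeks to 1 year; g of 0.05 to 0.20 for HUI-III; utility of 0.5 to 0.9; death between weeks 26 and 50 after a 24-week score was obtained.

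**1. Missing 24-week score, in units of g (unaided = 0, aided = 1)**

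A straight line from the unaided score to 1 year gives 24/52 = 0.4615 at week 24.

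First method:
- Complete data: (24/52)(0 + 1)/2 + (28/52)(1 + 1)/2 = 0.769
- Interpolated: (24/52)(0.4615)/2 + (28/52)(0.4615 + 1)/2 = 0.500
- Loss: 0.269g

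Second method, fitting at week 3 (4-week ramp, then 17 weeks at the 24-week level, then 28 weeks):
- Complete data: (4 × 1/2 + 17 + 28)/52 = 0.904
- Interpolated: (4 × 0.4615/2 + 17 × 0.4615 + 28 × 1.4615/2)/52 = 0.562
- Loss: 0.342g

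Second method, fitting at week 12 (8 weeks at the 24-week level):
- Complete data: (2 + 8 + 28)/52 = 0.731
- Interpolated: (4 × 0.4615/2 + 8 × 0.4615 + 28 × 1.4615/2)/52 = 0.482
- Loss: about 0.249g

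If the 1-year value is used for the missing score, it equals the true 24-week value under the constant-gain assumption, and the loss is 0 under both methods.

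For g = 0.05 to 0.20, the loss per affected patient is about 0.013 to 0.054 QALY (first method) or 0.017 to 0.068 QALY (second method, week 3).

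*Effect on an arm mean.* As an illustration, let 5% of 24-week scores be missing, borrowing the planned drop-out rate. The arm mean then moves by 0.05 × 0.342g, which is 0.0009 to 0.0034 QALY for the same range of g. Both arms receive a sound processor, so most of this cancels in the difference if gain and missingness are similar.

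**2. Death after the 24-week score, utility u, death at week t**

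- Credited by LOCF after week 24: (28/52)u
- Credited with zero from death: ((t − 24)/52)u
- Excess: ((52 − t)/52)u

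For u = 0.70 and t = 26, the excess is (26/52) × 0.70 = 0.35 QALY for that patient, and 0.35/53 = 0.0066 on the arm mean. Over u = 0.5 to 0.9 and t = 26 to 50 it runs from 0.019 to 0.45 QALY for the patient.

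**3. Both follow-up scores missing**

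The unaided score is carried to week 52, so the credited gain is 0 under either AUC method.

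**The case against.** The strongest reply is that the SAP never says the unaided score is an interpolation anchor. Its words can be read as letting the 1-year value stand in for the missing one, which fits the plateau in the closing paragraph and gives no loss. This stands. A reader might infer that the SAP prescribes interpolation from the unaided score, but the text does not say so. What remains is an unnamed anchor whose literal two-point reading conflicts with the section's own model of benefit.

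Second, the losses are shares of one patient's gain, whereas the analysis compares arms that both receive a processor. This also stands. Nothing in the documents suggests that missed 24-week visits would differ by arm, so it would be wrong to infer that the between-arm QALY difference is off by about a third.

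Third, the death gap is an omission, and the documents give neither expected mortality nor utilities. That limits how firmly it can be sized. It does not rescue the rule, which applies to every missing 1-year score.

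Fourth, SAP 5.1 promises sensitivity analyses if a significant amount of data is missing, comparable techniques in both groups, and an independent expert if parties disagree. The trigger is undefined, and the clause does not amend the specific rules in 4.2.5.6.

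**Conclusion.** The point holds as a correction to two stated rules in a tertiary analysis. Neither primary endpoint uses these values.

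- **24-week rule.** The loss per affected patient is between 0 and 0.342g, depending on the reading, the AUC method and the fitting date. The upper figure rests on a constant gain, fitting at week 3 and the unaided score as anchor. The effect on the difference between arms is small unless missingness differs by arm.
- **LOCF and death.** The rule as written gives a wrong HUI-III value for any patient who dies within the year. One death at week 26 with an assumed utility of 0.70 adds 0.35 QALY for that patient and about 0.007 to a 53-patient arm mean. The documents give no expected number of deaths, so the total cannot be stated.

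A reader might extend the death argument to APHAB. That does not follow: APHAB is not a utility and has no natural zero at death, so the SAP is simply silent there. Nor do the documents support a claim that multiple imputation is needed; that is a preference.

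**What to change.** Amend SAP 4.2.5.6 before database lock:

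1. State that a missing 24-week HUI-III or APHAB score takes the 1-year aided value, not a value interpolated from the unaided pre-surgery score.
2. Set HUI-III utility to 0 from the date of death, ahead of LOCF.
3. State separately how APHAB is handled after death.
4. State what is done when both follow-up scores are missing. Otherwise LOCF falls back on the unaided score by default.

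Multiple imputation may be added as a sensitivity analysis but is not required.

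The cost is a few sentences of SAP text and minor programming. No new data are needed: a death is a serious adverse event under protocol 7.4.3, so its date should already be in the safety data.

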4.3 Safety Variables

- Time to Loss of implant
- Adverse Events
 - Adverse Event (AE)
 - Adverse Device Effect (ADE), defined as AE with Probably or Definitely related to Study product
 - Serious Adverse Event (SAE)
 - Serious Adverse Device Effect (SADE), define as SAE with Probably or Definitely related to Study product
- Device deficiency by visit and divided by Not leading to SAE, Did lead to SAE and could have led to SAE.
- Removal of abutment

5 STATISTICAL METHODOLOGY

5.1 General Methodology

Continuous variables will be presented with Mean, Standard deviation (SD), 95% confidence interval (CI), Median, Min, Max and number of measures for both treatment groups and categorical variables will be presented with number and percentage.

Information about the methods used for the statistical testing can be found in the paragraphs below.

The primary analyses will be performed on the ITT population and the secondary and tertiary efficacy analyses will be performed on ITT and PP populations. The exploratory analyses are only performed for ITT population. Safety analyses will be performed on the safety population.

STATISTISKA KONSULTGRUPPEN		Statistical Analysis Plan	
Protocol: Clinical and health economic evaluation with a new Baha abutment design combined with a minimally invasive surgical technique		Protocol No: CBAS5439	
		Version: 1.0	Page 16 of 23

In case of significant amount of missing data, sensitivity analyses will be performed. Imputations will be made in the most appropriate way and the techniques used will be similar in the two groups. In case of disagreement between relevant parties, an independent expert will be consulted to ascertain that the method of imputation does not benefit or inhibit one group over the other.

The significance level of 0.05 will be split between the two primary analyses: combined endpoint 0.0499 and direct medical cost 0.0001. All other tests will be two-tailed and conducted at 0.05 significance level. All analyses will be performed by using SAS® v9.4 (Cary, NC).

5.2 Patient Disposition and Data Sets Analyzed

The number of subjects included in each of the ITT, PP and Safety populations will be summarised for each treatment group and overall. The number and percentage of subjects randomised and treated will be presented. Subjects who completed the study and subjects who withdrew from study prematurely will also be presented with a breakdown of the reasons for withdrawal by treatment group for the ITT, PP and Safety populations.

5.3 Protocol Violations/Deviations

Major protocol deviations are those that are considered to have an effect on the analysis. A list of potential major protocol deviations will be generated programmatically from the data captured before the clean file meeting. The clinical monitors of the study will review the list and the finalisation of the major protocol deviations will be done at the clean file meeting. The number of patients with major protocol deviations will be summarised per treatment group.

